1 Protocol details

4 List of Abbreviations and Definitions

(Delete as appropriate)

| AE | Adverse Event |
|-------------|--|
| AR | Adverse Reaction |
| ASR | Annual Safety Report |
| СА | Competent Authority |
| CI | Chief Investigator |
| CRF | Case Report Form |
| CRO | Contract Research Organisation |
| DMC | Data Monitoring Committee |
| EC | European Commission |
| GAfREC | Governance Arrangements for NHS Research Ethics Committees |
| ICF | Informed Consent Form |
| MA | Marketing Authorisation |
| MS | Member State |
| Main REC | Main Research Ethics Committee |
| NHS R&D | National Health Service Research & Development |
| PI | Principal Investigator |
| QA | Quality Assurance |
| QC | Quality Control |
| Participant | An individual who takes part in a clinical trial |
| REC | Research Ethics Committee |
| SAE | Serious Adverse Event |
| SDV | Source Document Verification |
| SOP | Standard Operating Procedure |
| SSA | Site Specific Assessment |
| TMG | Trial Management Group |
| TSC | Trial Steering Committee |

5 Summary/Synopsis

| Trial Title | Prospective study to correlate the treatment sensitivity of patient-derived organoids with clinical outcomes in head and neck squamous cell carcinoma (HNSCC) patients | |
|--|--|--|
| Internal ref. no. (or short title) | SOTO: treatment Sensitivity of Organoids to predict Treatment Outcome in head and neck cancer patients | |
| Protocol Version number and Date | Version 1.1 14 th March 2022 | |
| Study Phase if not mentioned in title | NA. It is an observation study | |
| IRAS Number | 305689 | |
| REC Reference | 22/NW/0023 | |
| Study Duration | 1 year of recruitment followed by standard of care follow-up for 5 years | |
| Sponsor name | King's College London | |
| | Guy's and St. Thomas Foundation | NHS trust (co-sponsor) |
| Chief Investigator | [name] | |
| Funder | Guy's and St Thomas' (GSTT) charity via a generous philanthropic donation from [name] and [name] | |
| Medical condition or disease under investigation | Head and neck squamous cell carcinoma (HNSCC) | |
| | Objectives | Endpoints |
| Primary | To assess the success rate of generating organoids from tissues in patients with HNSCC | Rates of successful organoid cultures |
| Secondary | 1) To assess the sensitivity of radiotherapy, cisplatin chemotherapy or cetuximab or their combination in PDOs | The ability of these treatment(s) to decrease tumour growth and kill the organoids ex-vivo (number and size of alive organoids after treatments) |
| | 2) To correlate the treatment sensitivities of PDOs above with the treatment outcome | To correlate the IC50 doses and dose response |

| | undergoing primary surgery and adjuvant radiotherapy +/- concurrent platinum chemotherapy (Cohort 1) | curves above with the recurrence rates and disease-free survival of patients |
|---|---|---|
| | 3) To correlate the treatment sensitivities of PDOs above with the treatment outcome of patients undergoing primary radiotherapy +/- platinum chemotherapy (Cohort 2) | The ability of the organoids to predict complete metabolic response and treatment outcome of patients |
| | 4) To correlate the sensitivities of platinum chemotherapy and/or cetuximab of PDOs or anti-PD1 with the treatment outcome of recurrent or metastatic HNSCC patients (Cohort 3) | The ability of the organoids to predict response to the same systemic treatments that the patients are receiving systemic treatments |
| Number of Subjects/Patients | 20 patients for year 1 pilot study | |
| Study Type | Observational | |
| Main Inclusion Criteria | Patients with head and neck squamous cell carcinoma undergoing curative treatment (primary surgery or radiotherapy) or presenting with recurrent or metastatic cancers Age > 18 years old | |
| Statistical Methodology and Analysis | This is a prospective study with a one-year pilot study aiming to recruit 20 patients, which is the realistic target for year 1. The results from year 1 will be used to estimate the sample size for future prospective observation study | |
| Human Tissue Samples (if applicable) | We will generate organoids from fresh tumour tissues and normal tissue when applicable and also stored unused biological samples in head and neck biobank for future translational research | |
| Data collected/storage (if applicable) | Patients' demographics, smoking and alcohol history, tumour characteristics, treatment details and responses, recurrences and survivals will be obtained from clinical | |

record and recorded on paper Case Report Forms (CRFs).

6 Introduction

Background

Head and neck cancers are a group of heterogeneous diseases and the most common histology being squamous cell carcinoma (1). Head and neck squamous cell carcinomas (HNSCC) tend to be associated with smoking and alcohol intake although there has been increasing incidence of oropharyngeal cancer due to HPV infection (2). Localized HNSCCs are usually treated with combined treatment modalities including surgery, radiotherapy and chemotherapy. HPV positive oropharygeal patients respond better to chemoradiation compared to HPV negative, tobacco-induced oropharyngeal cancer patients (2). These patients also have better 3-year rates of overall survival (82.4%, vs. 57.1%) compared with patients with HPV-negative tumours (3). Apart from HPV status, there is no accurate way of predicting which patients will be cured from radical treatment although patients with tumours which are resistant to radiotherapy +/- platinum cisplatin chemotherapy tend to present with locoregional recurrence and have a poorer outcome. There is no easy way to test radiosensitivity and chemosensitivity of these tumours. There is a need, therefore, to develop an accurate test to evaluate the sensitivity ex-vivo so that we can predict which patients are likely to be resistant to radiotherapy or platinum chemotherapy and therefore more likely to relapse. If so, treatment interventions such as radiation dose escalation, use of radiosensitising agents and/or other treatment strategies could be implemented.

Rationale of the study

Up to 50% of HNSCC patients may recur and the prognosis of these patients is less than one year. The first-line treatment for these patients is a platinum-based chemotherapy with cetuximab (4), which is toxic and only benefit a small number of patients. Although immunotherapy has shown great promise in recurrent or metastatic HNSCC as first-line or second-line treatments, only around 15-20% patients respond to these therapies with durable responses (5-6). There is therefore a need to ensure more effective radical curative treatment to prevent recurrences and to develop more effective targeted therapies for recurrent/metastatic HNSCC patients based on their genomic profiles.

Previously most of the preclinical models were largely based on immortalized cancer cell lines and xenografts studies from transformed cell lines. These techniques have been important in elucidating the mechanisms of late-stage tumour development as well as studying drug resistance. However, large-scale drug screens of transformed cell line panels have resulted in a high failure rate of preclinical compounds in clinical trials, which demonstrates the limitations of using these existing preclinical models based on transformed cell models. To this end, living biobanks consisting of tumour organoids, which facilitates the integration of genomic data with drug screening of patients' tumour samples to identify effective therapeutic regimens, have been established in a few tumour types including colorectal cancers, gastric cancers, liver cancers, breast cancers and more recently head and neck squamous cell carcinomas (7-10). The use of organoids in conjunction with genomic analysis from patient-derived tumour samples has the potential to stratify and identify effective

IRAS Ref : 305689

cancer therapies for individual patients by (a) comparing the response of individual tumours to specific drugs in order to provide personalized recommendations to manage patient care; (b) assessing how tumours respond and develop resistance to in order to further understand the mechanisms; (c) determining the next drug treatment option when standard clinical options are not available or not considered effective; (d) creating a database of drug sensitivity to tumour genetics to recommend potential therapeutic strategies.

In this study, we aim to assess whether PDOs can be used to predict treatment sensitivity in HNSCC patients.

7 Trial objectives and purpose

Overall aim

This study aims to generate patient-derived organoids (PDOs) from patients' tumour samples and to collect preliminary data on the ability of PDOs to predict patients' treatment response and whether their radiosensitivity and chemosensitivity can be correlated with their survival outcome.

Patient's cohorts

We will have three cohorts of HNSCC patients undergoing standard of care treatments:

1) Surgically resectable disease, followed by adjuvant radiotherapy +/- chemotherapy

2) Primary radiotherapy +/- concurrent chemotherapy

3) Recurrent or metastatic HNSCC undergoing platinum based chemotherapy +/- cetuximab

Primary objective

To assess the percentage of successful generated organoids from tissues in head and neck cancer patients

Secondary and exploratory objectives

Secondary objectives:

1) To assess the sensitivity of radiotherapy, platinum (cisplatin and/or carboplatin) chemotherapy or cetuximab or their combination in PDOs

2) To correlate the treatment sensitivities of PDOs above with the treatment outcome of patients undergoing *primary surgery and adjuvant radiotherapy* +/- concurrent platinum chemotherapy (*cohort 1*)

3) To correlate the treatment sensitivities of PDOs above with the treatment outcome of patients undergoing *primary radiotherapy* +/- platinum chemotherapy (*cohort 2*)

4) To correlate the sensitivities of platinum chemotherapy and/or cetuximab or immunotherapy of PDOs with the treatment outcome of *recurrent or metastatic* HNSCC patients (*cohort 3*)

Exploratory objectives:

1) To correlate the treatment sensitivities of PDOs with the detection rates of plasma ctDNA (all cohorts)

2) To assess and correlate the histopathological, genomic and transcriptomic features of patients' samples with PDOs

3) To assess the sensitivities of PDOs to various targeted therapies based on their genomic profiles

4) Collection of archival tissues, blood samples (whole or processed for ctDNA and PBMC), saliva (for ctDNA), urine or stool samples for other translational research

8 Study design & Flowchart

8.1 Study Design

This is a prospective observation study to generate patient-derived organoids from patients' samples to assess treatment response and to correlate with patients' treatment outcomes. We would first do a pilot study during year 1 to establish the pathways required and to assess the success rate in generating patient-derived organoids. During this time, we will also assess the willingness of patients to participate in the study, as well as that of clinicians to help recruitment. In addition, the time required to generate HNSCC organoids and to assess treatment response in order to correlate with patients' outcome will be evaluated during year 1.

Primary endpoint and outcome

Primary endpoint

The percentage of successful organoid samples generated from the tumour samples obtained

Primary outcome

The ability to generate organoid cultures successfully from tumour samples

Secondary endpoint and outcomes

Secondary endpoints

1) To determine the IC50 doses and dose response curves of radiotherapy, cisplatin or carboplatin chemotherapy and their combination of PDOs

2) To correlate the IC50 doses and dose response curves above with the recurrence rates and disease-free survival of patients

3) To correlate IC50 doses and dose response curves above with the complete metabolic response (PET-CT) and residual disease or salvage neck dissection

4) To correlate IC50 doses/dose response curves above with the objective response rates of patients undergoing same systemic treatment

Secondary outcomes

1) The ability of these treatment(s) to decrease tumour growth and kill the organoids ex-vivo (number and size of alive organoids after treatments)

2) The ability of the PDOs to predict recurrences and survival outcome of these patients based on the radiosensitivity and chemosensitivity of the PDOs

3) The ability of the organoids to predict complete metabolic response and treatment outcome of patients

4) The ability of the organoids to predict response to the same systemic treatments that the patients are receiving systemic treatments

Exploratory endpoints and outcomes

Exploratory endpoints

1) To correlate the IC50 doses/dose response curves with plasma ctDNA before and after treatment

2) Immunohistochemistry (IHC) staining, exome sequencing and RNA sequencing of PDOs and patients' samples

3) The IC50 doses of various targeted therapies based on actionable genetic mutations

4) To conduct further translational research using the patients' samples

Exploratory outcomes

1) The ability of the PDOs to predict minimal residual disease and persistent disease

2) The ability of the PDOs to recapitulate the histopathological and genomic features of human samples

3) The ability of the PDOs to predict responses to various targeted therapies based on genomic profiles

4) The ability of the PDOs to facilitate high quality translational research that will help to predict treatment response and bring benefit to patients

| Objectives | Endpoints/Measures | Outcomes |
|--|---|---|
| PRIMARY | | |
| 1) Compliance and acceptability of tissue sampling for the generation of organoids in head and neck cancer patients | Percentage of approached participants who consent to taking part | Rates of participants who agree to have samples taken to generate PDOs |
| 2) Ability to generate organoids from patients' tissues | Percentage of individuals whose successful organoid samples are obtained | Rates of successful organoid cultures |
| SECONDARY 1) To assess the sensitivity of radiotherapy, cisplatin chemotherapy or cetuximab or their combination in PDOs | Determine IC50 doses and dose response curves of radiotherapy, cisplatin chemotherapy and their combination of PDOs | The ability of these treatment(s) to decrease tumour growth and kill the organoids ex-vivo measured by the number and size of alive organoids after treatments. |
| 2) To correlate the treatment sensitivities of PDOs above with the treatment outcome of patients undergoing primary surgery and adjuvant radiotherapy +/- concurrent platinum chemotherapy (Cohort 1) | To correlate the IC50 doses and dose response curves above with the recurrence rates and disease-free survival of patients | The ability of the PDOs to predict recurrences and survival outcome of these patients based on the radiosensitivity and chemosensitivity of the PDOs |
| | Correlating IC50 doses and | The ability of the organoids to |

Table of endpoints/measures and outcomes

| the treatment outcome of patients undergoing primary radiotherapy +/- platinum chemotherapy (Cohort 2) 4) To correlate the sensitivities of platinum chemotherapy and/or | with the complete metabolic response (PET-CT) and residual disease or salvage neck dissection Correlating IC50 doses/dose response curves above with the objective response rates of patients undergoing same | predict complete metabolic response and treatment outcome of patients The ability of the organoids to predict response to the same systemic treatments that the patients are receiving systemic treatments |
|--|--|---|
| EXPLORATORY 1) To correlate the treatment sensitivities of PDOs with the detection rates of plasma ctDNA (all cohorts) | doses/dose response curves | The ability of the PDOs to predict minimal residual disease and persistent disease |
| 2) To assess and correlate the histopathological, genomic and transcriptomic features of patients' samples with PDOs | IHC staining, exome sequencing and RNA | The ability of the PDOs to recapitulate the histo- pathological and genomic features of human samples |
| | The IC50 doses of various targeted therapies based on | The ability of the PDOs to predict responses to various targeted therapies based on genomic profiles |
| blood (whole or processed for | translational research including TMB, PDL1 test, co- culturing of PDOs with PBMC to assess immunotherapy | The ability of the PDOs to facilitate high quality translational research that will help to predict treatment response and bring benefit to patients |

8.2 Treatment visits

This is an observation study and the patients will continue their clinical visits and follow-up for 5 years as per normal standard of care. We will obtain the treatment outcome from medical records of patients.

9 Subject selection

This will be a single centre study performed at King's College London and Guy's and St Thomas' NHS foundation trust.

We will have several cohorts of HNSCC patients undergoing standard of care treatments, which we plan to include:

- 1) 10 patients with surgically resectable locally advanced disease, followed by adjuvant radiotherapy +/- chemotherapy
- 2) 5 primary radiotherapy +/- concurrent chemotherapy
- 3) 5 recurrent or metastatic HNSCC undergoing platinum based chemotherapy +/- cetuximab or immunotherapy.

9.1 Subject inclusion criteria

- Patients with head and neck squamous cell carcinoma (including oral cavity, oropharynx, paranasal sinuses, hypopharynx or larynx) undergoing curative treatment (primary surgery or radiotherapy) or presenting with recurrent or metastatic cancers
- 2) Age > 18 years old

In addition, there are specific criteria for the three cohorts:

• Cohort 1:

Patients with surgically resectable locally advanced disease who will likely to undergo adjuvant radiotherapy +/- concurrent chemotherapy

• Cohort 2:

Patients suitable for primary radical radiotherapy +/- concurrent chemotherapy who agree to have additional research biopsy

• Cohort 3:

Patients with recurrent or metastatic disease who agree to have additional research biopsy

9.2 Subject exclusion criteria

1) Patients unable to give informed consent e.g. mental disability or vulnerable adults

10 Study procedures

10.1 Subject recruitment

Method of recruitment

The potential participants will be identified from MDT, surgical and oncology clinics and the initial approach to the potential participants will only be made by the direct care team members including those from surgical, oncology and radiology teams. HNSCC patients suspected to have primary or

IRAS Ref : 305689

recurrent HNSCC will be asked to consent to an additional research biopsy while undergoing an Examination Under Anaethesia (EUA) or biopsy or transoral robotic resection or biopsy as standard of care. This additional research biopsy will be used to generate PDOs in the lab. For those surgical resectable patients, we may ask for additional resected sample once adequate sample have been obtained for routine diagnostic purposes. For these patients, the resectable samples will be used to obtain more PDOs regardless of whether the biopsy samples were successful in generating PDOs. Moreover, for the surgical patients we will request specimens from the normal surrounding resected tissue to create normal tissue organoids to be used as the control. Once the PDOs are successfully generated in the lab, they will be tested for sensitivities to various treatments including radiotherapy, cisplatin/carboplatin and their combination for those organoids generated from HNSCC patients undergoing curative radical treatment and also platinum based chemotherapy +/- cetuximab or immunotherapy for those organoids generated from recurrent or metastatic HNSCC patients.

When the PDOs contain sufficient cells, these cells will be treated with increasing doses of radiotherapy and/or cisplatin chemotherapy and/or cetuximab in order to determine the IC50 and to obtain dose-response curves of these organoids to the treatments. In particular, we will treat the PDOs with the same treatments that the HNSCC patients receive in order to correlate the responses to radiotherapy and/or platinum chemotherapy +/- cetuximab or immunotherapy (co-cultured with immune cells). Successfully generated tumour organoids will be stored in the lab and can be used for future research.

The response of these HNSCC-PDOs will be compared to the actual tumour response to these treatments in these HNSCC patients:

1) Cohort 1: surgically resectable locally advanced disease

The tumours of these patients would have been surgically resected and so the responses of these organoids to radiotherapy and chemotherapy cannot be directly assessed. Most of these patients may then undergo adjuvant radiotherapy +/- concurrent chemotherapy. It is anticipated that the radiosensitivity and platinum chemosensitivity may correlate with the outcome of these patients. We will therefore assess whether those PDOs with lower IC50 would have longer disease-free survivals. If PDOs could be derived from both biopsy and resected samples from these patients, we will compare the differences in responses of these PDOs generated from either biopsy or resected samples. We will use the normal tissue organoids from the periphery of the surgical specimen to confirm that response to the treatments is tumour specific.

2) Cohort 2: Primary radiotherapy +/- platinum chemotherapy

We will culture HNSCC-PDOs and treat with irradiation and the same platinum chemotherapy drugs (cisplatin or carboplatin) as the corresponding patient. A few of these patients may undergo neoadjuvant chemotherapy before definitive chemoradiation. In this case, we will assess the responses and sensitivities of these organoids to the same chemotherapy drugs, usually docetaxel, cisplatin and 5FU (TPF). For patients undergoing primary radiotherapy with or without concurrent chemoradiation, PET-CT scan is done at 3 months after the completion of treatment to assess metabolic response. We will correlate the treatment sensitivity of PDOs as determined by the IC50 and dose-response curves with the complete metabolic responses by PET-CT scan and the rates of residual disease as well as salvage neck dissection.

3)Cohort 3: recurrent or metastatic HNSCC

The first-line treatment for the recurrent or metastatic HNSCC patients had been platinum-based chemotherapy +/- 5FU chemotherapy with or without cetuximab (oral cavity SCC only).

SOTO Study Protocol V1.1 (14/03/2022) REC Ref : 22/NW/0023

IRAS Ref : 305689

Translational research: Participants will be asked to give generic consent for their samples, derived organoids and/or cell lines and linked data to be transferred and used in future research. This includes the transfer and use of samples/data to KCL and its partners including the commercial sector and overseas organisations (including genetic research and whole genome sequencing). This will include the depositing of genetic and whole genome sequencing data in international repositories and participant-level data where it would not be possible to have data subsequently deleted.

Based on this consent, archival tissue, blood, saliva, oral swab, urine and stool samples will be stored at Guy's and St Thomas' head and neck biobank beyond the ethics approval date of the project and stored under the custodial of [name], biobank manager (HTA licence 12121; Licence Holder [name]). All material will be handled in accordance with the Human Tissue Act 2004 and other relevant legislation relating to the use of cell lines. Specific agreements will be put in place as required by the Sponsor including material transfer agreements where necessary.

SOTO Study Protocol V1.1 (14/03/2022) REC Ref: 22/NW/0023

IRAS Ref : 305689

Blood and other biological sample collection time points: We will ask patients to provide blood samples before (baseline) and at 3 months after the completion of their treatments. We may also request for up to additional 4 times during their treatment (e.g. at 3rd and 6th weeks of your radiotherapy) and follow-up (at 12 months after completion or at the event of recurrence), most likely at the same time that they are having blood tests as part of the standard procedures or occasionally as an additional procedure on each occasion, we will take up to 40ml of blood. We may also ask them to donate other samples such as saliva, oral swab, urine or faeces for future research at the same time points above.

Withdrawal of consent: The right of a participant to refuse participation without giving reasons will be respected. The participant will remain free to withdraw at any time from the trial without giving reasons and without prejudicing his/her further treatment and will be provided with a contact point where he/she may obtain further information about the trial. Patients will be made aware of the terms and conditions around withdrawal. If a patient withdraws from the study, the research team can retain any tissue samples, DNA/RNA samples and organoids/cell lines that have been created up until the time of the patient's withdrawal if the patient agrees. Any unused samples taken for research purpose can be destroyed if patients request to do so. Any demographic and medical information already provided or results from tests already performed on their samples will continue to be used in the study, however no further data or sample collection will be performed.

10.2 *Screening Procedures*

Potential eligible patients will be identified from surgical and/or oncology clinics and/or multidisciplinary meetings. These patients will be checked to see whether they will meet inclusion criteria. No extra screening investigations are needed for this study since this is an observation study. Patients will undergo routine standard of care investigations and treatments apart from consenting to this study and for their samples to be used for translational research during their routine standard of care procedures.

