10.4 Follow up Procedures

The follow-up procedures will be as per normal standard of care for 5 years and the schedule will not be changed due to this study. We will obtain relevant clinical information from the medical records.

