14.1 Data management

As this is an observation study, we will collect data from patients that are already available in the hospital record on patients' demographics, smoking and alcohol history, tumour characteristics including HPV status, proposed treatment plans. The patients' treatment details, treatment responses, recurrences and survivals will also be obtained from clinical record. They will be recorded on paper Case Report Forms (CRFs). Participant files and paper CRFs will be identified using a Participant Identification Number. Personal information will not be stored on CRFs. Screening and enrolment logs will be maintained by the research team. For enrolled participants, identifiable patient data will be stored in an Excel file for the purposes of gathering follow-up data. This file will password protected and stored on the KCL secured network, whereby access is only granted by the PI to named individuals. Paper CRFs, consent forms and the Trial Master File will be stored in locked filing cabinets within the Oral Clinical Research Unit (KCL, Guy's Hospital, London, UK). Data generated from laboratory processes related to the generation of PDOs and subsequent testing will

be kept in the research laboratory. These data will be identified with the PIN and no personal data will be used in the lab records.

Data linkage

If the participating patients have come from or will move to different health care providers, we will attempt to get either available archival tissues and/or data from the relevant health care providers after sending them the relevant patients' consent forms. We may also go to the central national databases with a patient's NHS number to get clinical data if necessary.

15 Statistical considerations

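### On withdrawal the protocol ends record-based outcome collection along with sampling, and does not ask whether the patient would still allow record access

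*Protocol*

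**What the plan says.** The withdrawal paragraph in the consent part of section 10.1 is the protocol's only rule on the matter. It is triggered by withdrawal from the study as a whole: "If a patient withdraws from the study, the research team can retain any tissue samples", along with nucleic acid samples and organoids made up to that point, provided the patient agrees. On data it says "Any demographic and medical information already provided or results from tests already performed on their samples will continue to be used in the study", and then "however no further data or sample collection will be performed". It adds "Patients will be made aware of the terms and conditions around withdrawal", without setting those terms out further.

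Outcome data need nothing from the patient. Section 8.2 says "We will obtain the treatment outcome from medical records of patients". Section 14.1 says "The patients' treatment details, treatment responses, recurrences and survivals will also be obtained from clinical record", and its data-linkage paragraph adds other care providers and national databases as possible sources. Section 10.4 says "The follow-up procedures will be as per normal standard of care for 5 years".

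The continuing research requests are for samples. Section 10.1 asks for blood at baseline and 3 months after treatment. Beyond that, "We may also request for up to additional 4 times during their treatment" and follow-up, with up to 40 ml each time and possibly saliva, swab, urine or faeces.

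Section 13.2 monitors withdrawal of consent as a single percentage. It plans no replacement once tissue has been obtained, on the ground that the primary outcome is unaffected. Section 13.3 separately monitors missed blood samples as a matter of protocol compliance.

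**The concern.** Secondary endpoints 2 to 4 in section 8.1 each need two things from the same patient: a tested organoid and a clinical outcome. The withdrawal rule treats the two differently. The patient is asked about keeping the organoid, but not about passive reading of the record. The study can therefore hold a usable organoid while its own rule bars it from collecting the outcome that organoid is to be compared with, even if the patient would have had no objection.

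The cohorts are very small (10, 5 and 5), so each missing outcome is a visible share of the data. Sampling may also be requested during radiotherapy and at recurrence, so it is plausible that those who withdraw differ in prognosis from those who stay. The protocol gives no data on this, and it should be read as a possibility only.

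**Working it through.** **Setting the provisions side by side**

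1. Trigger: withdrawal from the study (section 10.1). No sentence makes declining a sample a withdrawal. Samples are requested (section 10.1), and missed bloods are counted under compliance (section 13.3), apart from withdrawals (section 13.2).
2. Effect on material: existing samples and organoids may be kept with the patient's agreement.
3. Effect on data: what has already been obtained is kept and nothing further is collected. A recurrence recorded before withdrawal therefore stays in. What is lost is any response, recurrence or survival information not yet recorded.
4. Source of that information: medical records, with no patient contact (sections 8.2, 10.4 and 14.1). Continuing it would add no visits or procedures.
5. Section 13.2's reason for not replacing withdrawn patients covers the organoid success rate only. It does not address the outcome correlations.

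**Scale of one lost outcome**

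Inputs: cohort sizes 10, 5 and 5 (section 9), which sum to the stated 20 (synopsis), and an expected yield of at least 30% of tissue samples (section 15).

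*Case A: one sample per patient (assumed).* Expected patients with an organoid = n × 0.30.

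| Cohort | n | Expected with organoid |
|---|---|---|
| 1 | 10 | 3.0 |
| 2 | 5 | 1.5 |
| 3 | 5 | 1.5 |
| All | 20 | 6.0 |

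One lost outcome among these is 1/6 = 17% of all pairs, or 1/3 = 33% of the pairs if it falls in cohort 1.

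*Case B: every cohort 1 patient gives both biopsy and resected tissue, with independent success at 30% (assumed).* The chance of at least one organoid is 1 − 0.7² = 0.51. The expected number is 10 × 0.51 + 10 × 0.30 = 5.1 + 3.0 = 8.1. One lost outcome is 1/8.1 = 12%.

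**How often it might happen**

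The protocol states no withdrawal rate, so the rates w below are assumptions. The chance of at least one withdrawal among 20 is 1 − (1 − w)²⁰. Expected pairs under case A, if withdrawal is unrelated to organoid success and every withdrawal costs the outcome, are 6.0 × (1 − w).

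| Assumed w | At least one withdrawal in 20 | Expected pairs |
|---|---|---|
| 5% | 64% | 5.7 |
| 10% | 88% | 5.4 |
| 20% | 99% | 4.8 |

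These figures count all withdrawals. The share who would have allowed record access, which is the only share a change could recover, is unknown.

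**The case against.** A reader might infer that any patient who tires of giving samples has no route except full withdrawal and so drops out of follow-up. The documents do not support that. The rule applies to withdrawal from the study, samples are asked for rather than required, and section 13.3 tracks missed bloods separately. A patient who declines a draw appears to stay in, with record follow-up continuing. This part of the objection stands and limits the point to patients who do withdraw.

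A reader might also infer a demonstrated bias towards patients who do well. That is not supported either. No withdrawal rate or pattern is given, and a recurrence already recorded is retained.

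Four further objections carry weight:

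- Stopping new data collection after full withdrawal is a legitimate consent choice. That is right, and nothing here argues against it.
- The consent form is not available to this review and may already offer levels of withdrawal. If so, what remains is to bring the protocol text and the section 13.2 reporting into line with it.
- The sampling burden is modest. Two blood samples are firmly requested; the other four are optional and mostly expected to coincide with routine tests.
- The outcome correlations are preliminary, in a pilot without a formal power calculation, and section 13.2 is correct about the primary outcome.

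Together these keep the point small. They do not remove it: as written, the protocol stops record collection for every withdrawing patient without asking, and an analysis plan cannot restore outcomes that were never collected.

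**Conclusion.** The point holds in a limited form and is best labelled a cheap improvement. The single withdrawal rule ends passive outcome collection together with sampling. It gives the patient a say over retained organoids but none over continued record follow-up. A patient who withdraws but would have allowed record access loses whatever response, recurrence or survival data were not yet recorded.

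The primary endpoint is not affected and no stated figure changes. The benefit cannot be quantified from the document. The shares of about 1 in 6 and 1 in 8 pairs are illustrations that rest on the 30% floor for yield and on the assumed number of samples per patient. The point matters somewhat more if the study goes on to up to 4 further years of recruitment, as section 10.5 foresees, because the same wording would then carry into the larger outcome study.

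**What to change.** In the withdrawal paragraph of section 10.1:

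- State that declining or missing a sample is not withdrawal from the study.
- At withdrawal, ask the patient to choose between (a) stopping samples and contact, with record-based outcome collection continuing under consent, and (b) full withdrawal under the present rule.
- Record the choice on the CRF.

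In section 13.2, report the number at each level in place of one combined percentage, and say how withdrawal bears on the outcome endpoints as well as the primary one. Align the consent form if it does not already make this distinction.

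The cost is one extra question at withdrawal and amended wording in the protocol, the CRF and possibly the consent form. It could go into the major amendment already planned towards the end of year 1, or sooner if another amendment arises. The right to withdraw fully is unchanged.
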